10. APPENDICES

10.1. Appendix 1.1 Further Definition of Endpoints

Table 2 Response Criteria

Evaluation of lesions	
Complete Response (CR):	
Requires ALL of the following:
 
 1. Complete disappearance of all enhancing measurable and non-measurable disease sustained for at least 4 weeks. 2. No new lesions. 3. Stable or improved non-enhancing (T2/FLAIR) lesions. 4. Patients must be off corticosteroids (or on physiologic replacement doses only). 5. Patients must be stable or improved clinically.[£]
Partial Response (PR):	
Requires ALL of the following:
 
 1. Greater than or equal to 50% decrease compared to baseline in the sum of products of perpendicular diameters of all measurable enhancing lesions sustained for at least 4 weeks. 2. No progression of non-measurable disease. 3. No new lesions. 4. Stable or improved non-enhancing (T2/FLAIR) lesions on same or lower dose of corticosteroids compared to baseline scan. 5. The corticosteroid dose at the time of the scan evaluation should be no greater than the dose at time of baseline scan. 6. Patients must be stable or improved clinically.[£]
Progressive Disease (PD):	
Defined by ANY of the following:
 
 1. Greater than 25% increase in the sum of the products of perpendicular diameters of enhancing lesions compared to the smallest tumor measurement obtained either at baseline (if no decrease) or best response, on stable or increasing doses of corticosteroids.** 2. Significant increase in T2/FLAIR non-enhancing lesion on stable or increasing doses of corticosteroids compared to baseline scan or best response following initiation of therapy,* not due to co-morbid events (e.g. radiation therapy, demyelination, ischemic injury, infection, seizures, post-operative changes, or other treatment effects). 3. Any new lesion. 4. Clear clinical deterioration not attributable to other causes apart from the tumor (e.g. seizures, medication side effects, complications of therapy, cerebrovascular events, infection, etc.) or changes in corticosteroid dose.[£] 5. Failure to return for evaluation due to death or deteriorating condition. 6. Unequivocal progression of non-measurable disease.

Stable Disease (SD):	Requires ALL of the following: 1. Does not qualify for complete response, partial response, or progression. 2. Stable non-enhancing (T2/FLAIR) lesions on same or lower dose of corticosteroids compared to baseline scan. IN the event that the corticosteroid dose was increased for new symptoms and signs without confirmation of disease progression on neuroimaging, and subsequent follow-up imaging shows that this increase in corticosteroids was required because of disease progression, the last scan considered to show stable disease will be the scan obtained when the corticosteroid use was equivalent to the baseline dose. 3. Patients must be stable clinically. [£]
----------------------	--

*Patients with non-measurable disease only cannot have a complete or partial response. The best response possible is stable disease.

**Stable doses of corticosteroids include patients not on corticosteroids.

£ Clinical status will be assessed via ECOG Performance Score.

The table below provides the summary of the RANO response criteria.

Table 3 Overall Response

Criterion	Complete Response	Partial Response	Stable Disease	Progressive Disease
T1/Gd enhanced lesions	None	>50% decrease	<50% decrease to <25% increase	>25% increase*
T2/FLAIR	Stable or decreasing	Stable or decreasing	Stable or decreasing	Increasing*
New Lesion	None	None	None	Present*
Corticosteroids	None	Stable or decreasing	Stable or decreasing	NA**
Clinical Status#	Stable or improving	Stable or improving	Stable or improving	Worsening*
Requirement for Response	ALL	ALL	ALL	Any*

*Progressive Disease occurs when any of the criteria marked by * are present.

**Increase in corticosteroid dose in isolation of other criteria will not be taken into account in the assessment of progressive disease in the absence of persistent clinical status deterioration.

#Clinical status will be assessed via ECOG Performance Score

The best overall response (BOR) is the best response recorded from the start of the treatment until disease progression. Patients will have confirmatory radiographic scanning within approximately 4 weeks of initial results of partial or complete response (PR or CR) according to RANO. If not confirmed, response will be SD.

BOR rules are described as below based on the requirement of confirmed responses per RANO criteria.

BOR Based on Confirmed Responses

CR: Two objective statuses of CR a minimum of four weeks apart documented before progression and start of new anti-cancer therapy.

PR: Two objective statuses of PR or better (PR followed by PR or PR followed by CR) a minimum of four weeks apart documented before progression and start of new anti-cancer therapy, but not qualifying as CR. Sequences of PR- SD- PR are considered PRs as long as the two PR responses are observed at a minimum of 4 weeks apart.

SD: At least one objective status of stable or better documented at least 8 weeks after start date and before progression and the start of new anti-cancer therapy but not qualifying as CR or PR.

PD: Progression documented within 16 weeks after start date and not qualifying as CR, PR or SD.

Not Evaluable (NE): All other cases. Note that reasons for NE should be summarized and the following reasons could be used:

- Early death (Note: death prior to 8 weeks after start date)
- No post-baseline assessments
- All post-baseline assessments have overall response NE
- New anti-cancer therapy started before first post-baseline assessment
- SD too early (<8 weeks after start date)
- PD too late (>16 weeks after start date)

Special and rare cases where BOR is NE due to both early SD and late PD will be classified as 'SD too early'.

Derivation of BOR

The following table provides the derivation of BOR.

Table 3 Derivation of Best Overall Response when confirmation of response is required

Objective status at:

Assessment 1	Assessment 2	Assessment 3	Assessment 4	Overall Response
Death				NE
CR	CR	PD		CR
CR	NE	CR	PD	CR
PR	CR	CR	PD	CR
PR	CR	PD		PR
PR	PR	PD		PR
PR	SD or NE	PR	PD	PR
PR	PR	CR	PD	PR
CR	PR			Not allowed. Reappearance is progression
CR	PD or No or NE			SD
PR	PD or No or NE			SD
SD or NE	CR	PD		SD
SD or NE	PR	PD		SD
SD	PD			SD
PD				PD
No or NE assessment				NE
NE	PD			PD
NE	No or NE assessment			NE
NE	NE	PD		NE

Objective response rate (ORR) is defined as the proportion of patients with a documented complete response (CR) or partial response (PR) based on RANO criteria as determined by the investigator assessment collected in the CRFs, relative to the Full Analysis Set.

The DCR is the proportion of patients whose best overall response is CR, PR or SD based on RANO full analysis set. The best response of SD can be assigned if SD criteria were met at least once after first dose date at a minimum interval of 8 weeks from BBI608. New anti-cancer treatment will be derived based on Concomitant Medication if available.

Progression free survival (PFS) is defined as the time from the date of the first dose of any study drug to the date of PD, or death due to any cause, whichever comes first. If neither event has been observed, then the patient will be considered as censored. PFS (in months) will be calculated as $(\text{first event date} - \text{first dose date of any study drug} + 1) / 30.4375$. Sensitivity analyses for PFS may be conducted if deemed necessary.

Overall survival (OS) is defined as the time from the date of the first dose of any study drug to the date of death from any cause. Patients who are still alive at the time of the final observation, or who have become lost to follow-up will be censored at their last date of contact. OS in month is calculated as $(\text{date of death} - \text{first dose date of any study drug} + 1) / 30.4375$.

10.2. Appendix 1.2 Censoring for Time to Event Data

Table 4 summarizes the censoring rules for the PFS analysis and displays censoring hierarchy for this study. Table 5 shows the general reasons for PFS censoring and where the censoring hierarchy in **Table 4** came from.

Table 4 Event or Censor Time for PFS and Censoring Hierarchy

Censoring Hierarchy	Situation	Date of Event or Censor	Event / Censor
1	No baseline radiological tumor assessment available	Date of First Dose	Censored
2	New anticancer treatment started and no tumor progression	Date of previous adequate radiological assessment immediately prior to start of new therapy or Date of first dose, whichever comes later	Censored
3	Tumor progression (per RANO) documented after 2 scan intervals following previous adequate radiological tumor assessment	Date of previous adequate radiological assessment or Date of first dose, whichever comes later	Censored
4, 5	No tumor progression (per RANO) and subject lost to follow-up or withdrawal of consent	Date of last adequate radiological Assessment or Date of first dose, whichever comes later	Censored
6	No post baseline radiological tumor assessment available and no death reported within 2 scan intervals following the date of the first dose of study drug (BBI608)	Date of First Dose	Censored
7	No post baseline radiological tumor assessment available but death reported within 2 scan intervals following the date of the first dose of study drug (BBI608)	Date of Death	Event

	No tumor progression (per RANO) and no death reported within 2 scan intervals following last adequate radiological tumor assessment	Date of last adequate radiological tumor assessment or Date of first dose, whichever comes later	Censored
	No tumor progression (per RANO) but death reported within 2 scan intervals following last adequate radiological tumor assessment	Date of death	Event
	Tumor progression (per RANO) documented within 2 scan intervals following previous adequate radiological tumor assessment	Earliest of the target, non-target and new tumor assessment dates	Event

Notes: (1) Symptomatic deteriorations (i.e. symptomatic progressions, which are not radiographically confirmed) will not be considered as progressions.

(2) If target, non-target and new lesion assessments have different dates within a visit, then the earliest of those dates will be considered as the date of the tumor assessment if the assessment for that visit is progressive disease (PD); otherwise the latest date will be used.

(3) Adequate radiographical tumor assessment refers to an assessment with overall response of CR, PR, SD or PD.

(4) Comparing date of last tumor assessment to date of first dose is necessary if the last tumor assessment is baseline assessment

Table 5 PFS Censoring Reasons and Hierarchy

Hierarchy	Condition	Censoring Reason
1	No adequate baseline assessment	No adequate baseline assessment
2	Start of new anti-cancer therapy before event.	Start of new anti-cancer therapy
3	Event more than 2 weeks from last adequate post-baseline tumor assessment/start date	Event after missing assessments ^a
4	No event and [withdrawal of consent date \geq start date OR End of study (EOS) = Subject refused further FU]	Withdrawal of consent
5	No event and lost to follow-up in any disposition page	Lost to follow-up

6	No event and [EOS present OR disposition page for any EPOCH after screening says patient will not continue into any subsequent phase of the study] and no adequate post-baseline tumor assessment	No adequate post-baseline tumor assessment
7	No event and none of the conditions in the prior hierarchy are met	Ongoing without an event

For OS, patients last known to be alive are censored at date of last contact.

Date of Last Contact

The date of last contact will be derived for patients not known to have died at the analysis data cutoff date using the latest complete date (non-imputed) among the following:

- All patient assessment dates (e.g., blood draws [laboratory, PK], vital signs, performance status, ECG, tumor assessments, concomitant radiation, surgery)
- Start and end dates of follow-up anti-cancer therapies
- AE start and end dates
- Last date of contact where “Subject Remains in Follow-up” collected on the “Survival Follow-up” eCRF (do not use date of survival follow-up assessment unless status is alive)
- Study drug start and end dates
- Date of discontinuation on disposition eCRF pages (do not use if reason for discontinuation is lost to follow-up or death).

Note:

1. This list is not all inclusive and should be agreed upon by the study team according to the data collected in the CRF
2. Only dates associated with patient visits or actual examinations of the patient should be used. Dates associated with a technical operation unrelated to patient status (e.g., the date a blood sample was processed) should not be used.
3. Assessment dates after the cutoff date will not be applied to derive the last contact date.

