7.4. Dropouts

Time to event parameters will be censored if patients drop out (withdraw from consent or lost to follow-up) before documentation of the events (progressive disease / death). Rules for censoring for PFS are detailed in 10.2

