8.2.2.2. Progression Free Survival at 6 months (PFS-6, Phase 1 and Phase 2)

PFS data will be analyzed by arm. PFS summary in Arm B will be provided only when the number of patients in that arm is at least 10. The same rule applies to Arm A data.

Progression free survival at 6 months (PFS-6) is defined as the proportion of patients who have survived without objective disease progression per RANO criteria for at least 6 months after enrollment. The censoring rules for PFS will be detailed in 10.2. If a patient has not progressed or died at the time of analysis, PFS will be censored on the date of the last tumor assessment. This includes patients who are lost to follow-up or have withdrawn consent.

PFS in months is calculated as (first event date/censored date – date of first dose of any study drug + 1)/30.4375. Estimates of the PFS curves at 6 months will be obtained using the Kaplan-Meier method and will be presented along with the 80% CI using the normal approximation to the log transformed cumulative hazard rate.

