8.2.3. Analyses for Secondary Endpoints

8.2.3.1. Other Efficacy Endpoints Analysis

Response data (including Disease Control Rate (DCR) and Objective Response Rate (ORR)), progression free survival (PFS) and overall survival (OS) data will be analyzed by arm. Response data summary for Arm B will be provided only when the number of patients in that arm is at least 5. The same rule applies to Arm A data. Otherwise, only response data listing will be provided.

Summary for survival data (including PFS and OS) will follow the rule of ‘at least 10’ as described in Section 8.2.2.2.

DCR is defined as the proportion of patients with a documented complete response, partial response, and stable disease (CR + PR + SD) based on RANO. The primary estimate of DCR will be based on the FAS population. DCR will be summarized for each treatment arm along with the corresponding exact 2-sided 95% CI using the Clopper Pearson method.

ORR is defined as the proportion of patients with a documented complete response and partial response (CR + PR) based on RANO. The primary estimate for ORR will be based on the FAS population.

ORR will be analyzed similarly as DCR. Best Overall Response (BOR) will also be summarized in a similar fashion.

PFS in the full analysis set is defined as the time from exposure to any study drug to the first objective documentation of disease progression or death due to any cause. If a patient has not progressed or died at the time of analysis, PFS will be censored on the date of the last tumor assessment. PFS is calculated as described in section 8.2.2.2.

PFS will be reported as the median event time (and other quartiles) and the corresponding 2-sided 95% CI for each treatment arm. Estimates of the PFS curves obtained from the Kaplan-Meier method will be presented along with a graphical presentation of PFS curves.

OS is defined as the time from exposure to any study drug to death from any cause. Patients who are alive at the time of analysis or who have dropped out will be censored at their last date known to be alive. OS in months is calculated as $(\text{date of death/Last known to be alive date} - \text{date of first dose of any study drug} + 1)/30.4375$.

The survival experience of patients will be summarized by the Kaplan-Meier method.

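### SAP 10.2 Table 4, row 4,5: the PFS censoring rule for lost or withdrawn patients has no condition on death, so it contradicts a later row of the same table and could censor known deaths in PFS-6

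*SAP*

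**What the plan says.** **Table 4 (SAP 10.2), row 4,5.** The condition is "No tumor progression (per RANO) and subject lost to follow-up or withdrawal of consent". The result is censoring at the last adequate radiological assessment or first dose, whichever is later.

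**Table 4, later row.** The condition is "No tumor progression (per RANO) but death reported within 2 scan intervals following last adequate radiological tumor assessment". The result is an event on the date of death. A parallel row makes death an event when there is no post-baseline scan and the death falls within two scan intervals of first dose.

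**Table 5 (SAP 10.2).** The text above Table 4 reads "Table 5 shows the general reasons for PFS censoring and where the censoring hierarchy in" Table 4 came from. Item 4 begins "No event and [withdrawal of consent date" and item 5 reads "No event and lost to follow-up in any disposition page".

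**SAP 8.2.2.2 (PFS-6).** "If a patient has not progressed or died at the time of analysis, PFS will be censored on the date of the last tumor assessment". The next sentence applies this to lost and withdrawn patients, and the section points to 10.2 for the censoring rules. The PFS definition in SAP 10.1 likewise censors only when neither progression nor death has been seen.

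**SAP 7.4.** "Time to event parameters will be censored if patients drop out (withdraw from consent or lost to follow-up) before documentation of the events", followed by a parenthesis naming progressive disease and death. It too points to 10.2 for PFS.

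**OS.** SAP 8.2.3.1 says "Patients who are alive at the time of analysis or who have dropped out will be censored at their last date known to be alive", and 10.1 has a similar phrase about loss to follow-up. SAP 10.2 limits OS censoring to patients last known to be alive, and derives the last-contact date only for patients not known to have died.

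**The concern.** One patient can satisfy two rows of Table 4 that give opposite results. The table is headed as a hierarchy, and row 4,5 is listed above every row that counts a death. A programmer who works down the table would censor the patient; one who works from Table 5 items 4 and 5 or from 8.2.2.2 would count an event.

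The choice affects the primary endpoint in a predictable direction. Patients with recurrent glioblastoma may leave a study because they are getting worse. Note (1) under Table 4 says that symptomatic deterioration without radiographic confirmation is not progression, so death may be the only PFS event such a patient can still have. Replacing that death with censoring at the last scan is informative and raises the Kaplan-Meier estimate at 6 months.

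**Working it through.** **1. One patient under each rule.** Take an Arm B patient with stable disease on the day 56 scan, consent withdrawn on day 60, and a recorded death on day 66. The death is 10 days after the scan. Scans are every 8 weeks (SAP 2.1), so two scan intervals are 2 × 8 = 16 weeks.

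| Rule | Result |
|---|---|
| Table 4 row 4,5 | Censored, day 56 |
| Table 4 later death row | Event, day 66 |
| Table 5 items 4 and 5 | Do not apply, because there is an event |
| SAP 8.2.2.2 and 10.1 | Event, day 66 |

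The conflict rests on this overlap. It does not rest on the rank numbers of the lower rows, which may be displaced in the extracted table.

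**2. The plan's own figure.** SAP 4.2.2 gives n = 30, a projected PFS-6 of 20% and a two-sided 80% exact interval. For 6/30 the Clopper-Pearson interval is 10.86% to 32.47%, so the stated lower bound above 10% reproduces. It is a planning figure and does not depend on row 4,5.

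**3. Size of the bias, hazard model.** All hazards are assumptions:
- progression 0.0085 per day, seen at the next 56-day scan;
- death 0.001 per day;
- scans on days 56, 112 and 168;
- 6 months = 6 × 30.4375 = 182.6 days (month length from SAP 8.2.2.2).

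All deaths counted: exp(−0.0085 × 168) × exp(−0.001 × 182.6) = 0.2398 × 0.8331 = 0.1998, or 20.0%.

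Every PFS death censored at the previous scan: the death term drops out, leaving exp(−1.428) = 0.2398, or 24.0% (23.9% by simulation).

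Death is the PFS event in 13.2% of simulated patients. Censoring deaths in 5% or 10% of all patients therefore means that 5/13.2 = 38% or 10/13.2 = 76% of PFS deaths follow withdrawal or loss.
- 5%: 21.3% by simulation. Approximate check: 0.2398 × exp(−0.1826 × 0.621) = 0.2141.
- 10%: 22.8% by simulation. Approximate check: 0.2398 × exp(−0.1826 × 0.242) = 0.2294.

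**4. The same question for one arm of 30.** Assume 24 events before 6 months at exponential quantiles, so Kaplan-Meier PFS-6 is 20.0% (80% CI 11.6% to 30.0% on the log cumulative hazard scale). Now change k of the 24 events, assumed to be deaths, to censored. If they are censored at first dose, the estimate is 6/(30 − k). If they are censored at the last 8-weekly scan, it depends on which events are drawn; the last column is the largest value over 2,000 random draws.

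| k | Censored at first dose | Largest value, censored at last scan |
|---|---|---|
| 1 | 6/29 = 20.7% | 23.3% |
| 2 | 6/28 = 21.4% | 25.7% |
| 3 | 6/27 = 22.2% | 28.5% |

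With row 4,5 made conditional on no death, it censors none of these deaths and the estimate stays at 20.0%.

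**The case against.** **The rest of the SAP counts these deaths.** Table 5, named as the source of the hierarchy, opens both matching items with a no-event condition, and 8.2.2.2 and 10.1 agree. This stands. A reader might infer from row 4,5 that the plan's settled rule is to remove known deaths from PFS-6; the documents do not support that. They show an internal contradiction in which most of the text favours counting the death. It still needs correcting, because 7.4 and 8.2.2.2 both refer the reader to the section that holds the faulty row. Table 5 is not a clean tie-breaker either: its item 3 limits events to two weeks from the last assessment where Table 4 uses two scan intervals. That is a separate mismatch.

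**The patient may already have progressed.** RANO progression criterion 5 (Protocol 9.3, SAP Table 2) includes failure to return because of death or deterioration, so row 4,5 might not apply. This is arguable. Against it, note (1) excludes unconfirmed symptomatic deterioration, and Table 4 has rows for death without tumor progression, which would have little purpose if death itself were progression.

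**The deaths may not be known.** Protocol 5.6 collects survival by record review but does not say that this continues after consent is withdrawn, and a lost patient's status may never be learned. This stands, and it limits how many patients are affected.

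**OS.** A reader might extend the point to OS. Table 4 is a PFS table, and 10.2 limits OS censoring to patients last known to be alive. Only two loose phrases, in 8.2.3.1 and 10.1, remain. SAP 7.4 is consistent with counting deaths and need not be called an error.

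**Conclusion.** The contradiction is real and touches the primary endpoint, but its scope is limited. It concerns patients without RANO progression who are lost or withdraw and are then known to have died within 16 weeks of the last adequate assessment, or of first dose if there is none. The row does not reach every dropout, and later deaths are censored by other Table 4 rows anyway.

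If row 4,5 is programmed literally, PFS-6 is biased upward. From a true value of about 20%, the hazard model gives about 21.3% or 22.8% when deaths in 5% or 10% of patients are censored, and at most about 24% when every PFS death is. A larger effect might be imagined if a fifth of patients were affected, but under these hazards only 13.2% have death as their PFS event. The hazards, the 8-weekly scans counted from first dose (as in Arm B) and the affected shares are assumptions, since the documents give no dropout rate.

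The bias should not be set against the margin between 10.9% and 10% in the sample-size statement. That bound does not depend on this row, and SAP 4.1 states that there is no hypothesis testing.

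**What to change.** - **Table 4, row 4,5:** add *and no death reported within 2 scan intervals of the last adequate assessment (or of first dose if none)*. This matches the no-event condition in Table 5 items 4 and 5 and the form of the other Table 4 rows.
- **OS wording, secondary:** in SAP 8.2.3.1, after the phrase on patients who have dropped out, and in SAP 10.1, after the phrase on loss to follow-up, add *and are not known to have died*. This brings both into line with 10.2.
- **SAP 7.4:** no change needed.

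The cost is one clause in Table 4 and a short phrase in each of two OS sentences. No new data are needed. The change should be made before the PFS derivation is programmed or, if it already has been, the program should be checked against the corrected row.
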